1.7 Sponsor Details: Sheffield Teaching Hospitals NHS Foundation Trust
[name]
[contact]
[contact]

Protocol Signature Page

Role	Name	Signature
Principal Investigator	[name]
Co-Investigator	[name]
Co-Investigator	[name]
Co-Investigator	[name]
Co-Investigator	[name]
Co-Investigator	[name]
Co-Investigator	[name]
Co-Investigator	[name]

Principal Investigator Signature:

I confirm that I have read and understood protocol (Version Dated). I agree to comply with the study protocol, research governance, clinical trial regulations and appropriate reporting requirements.

Signature:

Date:

Print Name:

2 Scientific Summary

Background

Motor neurone disease (MND) is a neurodegenerative illness which causes progressive paralysis of muscles leading to death usually within 3 years of diagnosis. Dysphagia is a common problem in patients with MND, and causes difficulties in maintaining a safe and adequate oral intake of food and fluids. Gastrostomy feeding tubes are commonly used to support patients with dysphagia. The current practice of gastrostomy feeding is largely based on consensus and expert opinion rather than the outcomes of appropriately designed trials. There is lack of evidence to indicate the optimal timing for gastrostomy or which method of gastrostomy insertion is most appropriate. Additionally high quality evidence regarding survival and quality of life following gastrostomy insertion is lacking.

Aims

- i) Identify the current practice with regard to gastrostomy insertion in MND Care Centres within the UK and compare it with the practice in the Sheffield and Leeds MND Care & Research Centres.
- ii) Identify the most appropriate method for gastrostomy insertion in patients with MND.
- iii) Identify the optimal timing for gastrostomy use in patients with MND.
- iv) Compare outcomes between different gastrostomy protocols within and between centres with regard to (a) survival; (b) complications; (c) change in weight; (d) change in quality of life; and (e) carer burden, post gastrostomy.
- v) Develop guidelines for gastrostomy use in patients with MND.

Plan of Investigation

Patients will be prospectively recruited into PROGAS when a decision to refer a patient for gastrostomy is made. The recruitment target is 504 patients over 21 months. Questionnaires will be completed collecting disease-related data, details of the procedure and complications. Over the subsequent 12 month period, data will be collected on complications, quality of life, and carer burden. A qualitative study will be conducted at the Leeds and Sheffield sites which will assess the outcomes of gastrostomy from the perspectives of the patients, and their carers; delineate their concerns, problems and needs; and enhance our understanding of the factors that are associated with gastrostomy feeding and impact on the quality of life.

Potential Impact

The project addresses an area of unmet need of key strategic importance which has been identified as a research priority by the Dementias & Neurodegenerative Diseases Research Network. The results of this work will translate into the development of guidelines for gastrostomy insertion use in patients with Motor Neurone Disease locally within the regional MND centres in Sheffield and Leeds. Additionally this work may inform guidelines nationally. The principles will be readily applicable to patients with severe dysphagia symptoms who are eligible for gastrostomy insertion due to other neurological diseases. Once a need for gastrostomy has been established, these guidelines will provide recommendations for optimising benefit and the patient and carer experience of gastrostomy.

3 Lay / Plain English Summary

Motor neurone disease (MND) is a devastating illness which leads to progressive muscle weakness and eventual death, usually within 3 years. Difficulty in swallowing is a common problem in patients with MND. Patients with severe swallowing difficulty experience malnutrition, dehydration, choking and an increased risk of chest infections. Long-term nutritional support of patients with severe swallowing difficulty can be achieved by placing a feeding tube, known as a gastrostomy, directly into the stomach. However, the current practice of gastrostomy feeding is largely based on consensus and expert opinion rather than the outcomes of appropriately designed trials. Currently gastrostomy technique and timing of insertion within the disease course vary throughout the UK. There is a lack of evidence to suggest what the optimal timing for gastrostomy is, or which method is most appropriate. In addition, although gastrostomy is routinely performed, the benefits, such as improved survival and quality of life following gastrostomy, have not been proven.

The main aim of this study is to develop evidence-based guidelines for gastrostomy use in patients with MND.

Patients and carers will be recruited at the participating MND Centres in Sheffield, Leeds and around the UK. Questionnaires will be used to assess the safety, complications and benefits of the differing timings and methods of gastrostomy insertion. Participants recruited at the Leeds and Sheffield MND Centres will take part in an additional interview study, to further explore the perceptions and experiences of patients and carers with regard to the impact of gastrostomy on quality of life.

The results of this work will translate into the development of guidelines, which will optimise the benefit, and the patient and carer experience of gastrostomy. The principles will be readily applicable to patients with severe swallowing problems who are eligible for gastrostomy insertion due to other neurological diseases.

4 Research Aims & Hypotheses

The overall aim is to produce evidence based guidelines which will optimise the standard of care of patients with MND requiring gastrostomy. In order to do this we aim to:

- i) *Identify the current practice with regard to gastrostomy insertion in MND care centres within the UK and compare it with the practice in the Sheffield and Leeds MND Care & Research Centres.*

There are currently no evidence based guidelines for the management of dysphagia in patients with MND [1]. Consequently we hypothesise that practice around the country will vary with regard to indication and method of insertion for gastrostomy for MND patients. We aim to carry out a survey to assess the variation in practice and identify good practice points. The results of the survey will inform the design of the main prospective component of PROGAS.

- ii) *Identify the most appropriate method for gastrostomy insertion in patients with MND.*

The literature is inconclusive with regards to which method of gastrostomy is preferable for patients with MND. We hypothesise that PIG/RIG procedures are safer for patients with MND and will result in reduced one month mortality, in this patient group.

- iii) *Identify the optimal timing for gastrostomy use in patients with MND.*

The American Academy of Neurology Practice Parameter for ALS suggests that gastrostomy insertion should be performed before FVC falls below 50% [2]. However, there are no specific evidence based guidelines on when in the course of MND a gastrostomy should be inserted. We hypothesise that patients undergoing gastrostomy before malnutrition or with early dysphagia symptoms will have an improved survival compared to patients who have gastrostomy insertion when significant malnutrition and dysphagia have occurred.

- iv) *Identify the effect on quality of life of gastrostomy.*

The evidence regarding improvement in quality of life following gastrostomy is inconclusive [1]. We hypothesise that gastrostomy feeding is associated with an improvement in quality of life of the patient. We will also assess the quality of life and views of the carers regarding the gastrostomy.

- v) *Identify the effect on nutritional status of gastrostomy.*

The evidence regarding an improvement in nutritional status is inconclusive [1]. We hypothesise that gastrostomy feeding is associated with an improvement in nutritional status.

- vi) *Identify the complication rate associated with the various gastrostomy protocols.*

We hypothesise that the different gastrostomy techniques are associated with differing complication rates such as post procedure infection, respiratory complications, tube displacement, and tube falling out.

5 Nature of Project

PROGAS has been designed in response to particular uncertainties faced by ourselves as healthcare practitioners, and as a result of the research priorities identified by the Dementias and Neurodegenerative Diseases Research Network (DeNDRoN) Clinical Studies Group for MND and the Motor Neurone Disease Association (MNDA). For PROGAS we have adopted an all-inclusive approach, inviting as many MND care centres in the UK, as possible. Following ethical and research governance approvals, PROGAS will run for 3 years. Participant recruitment will occur for the first 21 months. The follow up period will take 12 months. Finally, a 3-month period at the end of the project will enable analysis of data, dissemination of findings and report writing. A more detailed project timetable is available in section 19 of this protocol.

A mixed methodology approach will be employed:

(a) Quantitative questionnaires will be used to evaluate the UK clinical practice in relation to gastrostomy in patients with MND.

(b) Qualitative interviews will be used to illuminate unexplored issues surrounding the experience of patients, and their informal carers, with regard to gastrostomy and its impact on quality of life.

We have chosen this methodology approach as it enables us to use quantitative questionnaires designed to investigate issues apparent from our pilot work and clinical experience, as well as allowing the opportunity for new, previously unrecognised issues important to the patient and the carer to be identified and explored through qualitative interviews. The quantitative part of the study will form the main study and will be conducted with participants (i.e., patients and their carers) from all participating sites. The qualitative part of the study will form a smaller component and will be conducted only at the MND Care and Research Centres in Sheffield and Leeds, with patients and their informal carers.

6 Background and Rationale

Background

Motor neurone disease (MND) is the third commonest adult onset neurodegenerative disorder with an annual incidence of 2 in 100,000 and prevalence of 5-7 in 100,000 [3]. MND causes progressive weakness and wasting of muscles controlling movement, breathing and swallowing due to a degeneration of the innervating motor neurones. The cause of the motor neurone death is unknown and currently there are no effective treatments to prevent progression which on average leads to death with 2-3 years of diagnosis [3]. Evidence suggests that Riluzole, an anti-glutamate drug, slows progression by approximately 3 months [4] and non-invasive ventilation (NIV) has been demonstrated to prolong average survival by up to 7 months [5]. Specialist multidisciplinary clinics provide disease-management and palliative care services aiming to alleviate symptoms, maximise function, and to improve quality of life by means of reducing psychological distress and maintaining the autonomy of patients as long as possible [6-11].

Dysphagia, difficulty in swallowing, is a common problem in patients with MND [12, 13] and can present relatively early on in the disease course in patients with bulbar onset MND. Dysphagia results from weakness of the tongue, muscles of mastication and swallowing, as well as from loss of co-ordination of the chewing and swallowing actions [14]. Patients with severe dysphagia experience malnutrition and dehydration; continued weight loss; distressing choking and coughing on attempts to swallow; slow, prolonged and effortful

mealtimes which are a burden on the patient and carer; and frequent aspiration which increases the risk of recurring chest infections and pneumonia [12, 13, 15-17]. Malnutrition is associated with shortened survival rates [4, 18, 19]. The management of nutritional status and dysphagia is, consequently, a major aspect of the multi-disciplinary care provided to patients with MND [20]. Dysphagia management in MND aims to provide patients with an adequate calorific intake, in a safe manner, while maintaining their quality of life as much as possible [20]. When patients experience early symptoms of dysphagia simple measures can be employed, such as introducing soft, moist, easy to swallow food and thickened fluids [21, 22], together with teaching patients safe-swallowing techniques (e.g., to concentrate on eating and drinking, to avoid speaking and laughing with food in the mouth, and adopt an ideal head position when eating) [11, 22]. With disease progression, enteral tube feeding becomes necessary and is frequently used as a means of delivering an adequate protein and calorific intake in a safe manner [12, 13, 15-17]; hence, preventing malnutrition and dehydration as well as stabilising body weight [23]. Enteral tube feeding in patients with dysphagia can be delivered either via nasogastric tube (NGT) or gastrostomy insertion. Gastrostomy is favoured over NGT as problems with tubes falling out, migrating tubes causing aspiration, nasal discomfort and poor cosmesis make NGT a poor long term solution [14, 20]. Additionally, survival post gastrostomy was superior in a small retrospective review of gastrostomy versus NGT [24].

Current practice regarding the next phase of dysphagia management using gastrostomy feeding is largely based on consensus and expert opinion rather than the outcomes of appropriately designed trials. There is currently an ongoing debate in relation to the impact of gastrostomy tube placement on survival for patients with MND. Evidence suggests that there is a benefit in survival for patients with gastrostomy; however, this evidence is weak and inconclusive [1]. In addition, although gastrostomy placement is widely considered to have a beneficial impact on the nutritional outcome for patients with MND, there is little evidence to support this conclusion [1]. The effect of gastrostomy on quality of life for patients with MND remains largely unexplored [1], although consensus exists among neurologists that this intervention improves quality of life and should be offered to patients when indicated [11, 21]. There is recent indirect evidence to suggest quality of life benefits following gastrostomy but this has not been studied as a primary outcome [25]. The American Academy of Neurologists (AAN) and European Federation of Neurological Societies both recommend gastrostomy feeding for MND patients [2, 21]. However, there is currently no common consensus on the timing of gastrostomy [1]. The AAN recommend gastrostomy when either BMI < 18.5 kg/m², weight loss of at least 10% from pre-morbid weight, or dysphagia graded 6/10 on the ALS severity scale [2].

There are several methods of gastrostomy insertion described in the MND literature; percutaneous endoscopic gastrostomy (PEG) [1, 26-34]; percutaneous radiologic gastrostomy (PRG), also known as radiologically inserted gastrostomy (RIG) [24, 34-38]; and per-oral image-guided gastrostomy (PIG) [29]. Percutaneous endoscopic gastrostomy (PEG) is the most commonly used method for gastrostomy insertion in MND patients [8, 20]. Normally, it is a relatively quick and easy procedure, performed under endoscopic guidance using conscious sedation. However, there are certain limitations and risks for MND patients associated with a PEG insertion. Patients with MND are at risk of aspiration due to bulbar muscle dysfunction, and the risk is further increased during a PEG insertion procedure. This is a result of the sedation and pharyngeal anaesthesia required for the procedure, as well as of the weak anti reflux mechanism [39, 40]. In addition, a “high riding” stomach in MND patients, due to diaphragmatic muscle weakness, can make transillumination of anterior abdominal wall difficult during the procedure, thus increasing the risk of complications [37]. PEG insertion is unsuitable for the patients with moderate to severe respiratory dysfunction (FVC 30-50% of predicted), as the positioning of the patient, laryngospasm, and sedation

required put the patient at high risk of significant respiratory compromise [41-43]. Often such patients will be dependent on non-invasive ventilation (NIV) and it is impractical to perform standard PEG placement with NIV in place.

A pure percutaneous technique, percutaneous radiologic gastrostomy (PRG) also known as radiologically inserted gastrostomy (RIG), has been alternatively used in patients with MND. PRG/RIG is considered a safe intervention with low complication rates [30, 34, 35]. PRG/RIG does not require conscious sedation or endoscope use; instead, it is performed by initial insufflation of air into the stomach, followed by tube insertion under fluoroscopic guidance [30]. A modified per oral technique, per-oral image-guided gastrostomy (PIG), has not been widely used in the management of dysphagia in patients with MND, although it has been used in other disease areas, such as stroke, multiple sclerosis and malignant disorders involving upper gastrointestinal tract [44]. PIG is a hybrid technique, requiring minimal conscious sedation, in which the stomach is punctured under fluoroscopic guidance, following which the oesophagus is catheterised in a retrograde fashion using a guide wire. The gastrostomy tube is then passed over the guidewire, through the mouth, oesophagus and out through the abdominal wall. Evidence suggests that PIG combines the advantages of PEG and PRG/RIG constituting an effective alternative method of gastrostomy with better long-term clinical outcomes in terms of success, re-intervention and complication rate [44].

The AAN guidance recognising the increased risk of a PEG procedure in patients with significant respiratory compromise, suggests that gastrostomy should be performed before the FVC falls below 50% [2]. Alternative methods, such as PRG/RIG and PIG, may offer advantages particularly in patients with significant respiratory compromise. In addition, the application of NIV during gastrostomy procedures [36] and newer sedative agents, such as Remifentanyl [45], may also allow a later successful and safe insertion of gastrostomy. There is little evidence in the MND literature to suggest what the optimal timing for gastrostomy is or which of the gastrostomy insertion methods is superior in a given situation [1, 46]. Consequently, multiple gastrostomy techniques and timings of gastrostomy insertions, within the disease course of MND are used throughout the UK. There is a consensus and it is our hypothesis that PRG/RIG and PIG procedures are a safer gastrostomy technique in patients with MND than PEG, particularly if there is any degree of respiratory compromise. One small prospective study [30] reported that there was a significant difference ($p = 0.004$) between survival in PEG patients and survival in RIG patients, but this was in the subgroup of patients with respiratory failure. The median survival after gastrostomy was 140% higher in the RIG group compared to PEG group. There are few studies in the MND literature comparing survival time or one month post procedure mortality of patients with MND following different methods of gastrostomy. Three recent studies [24, 34, 47] reported that there was no significant difference in survival between PEG patients and RIG patients. These studies were retrospective, comprised small numbers and were not adequately powered to detect potentially important clinical differences. Given the lack of comparative studies we have reviewed the literature for mortality data. For MND patients undergoing PEG the 30 day mortality rates range from 4% to 25% [19, 26, 30-32, 47-51]. For MND patients undergoing RIG procedures the 30 day mortality rate ranges from 4% to 9% [30, 35, 47].

MND care in the UK is largely delivered by multi-disciplinary teams, led by a consultant neurologist, within Motor Neurone Disease Association funded MND Care and Research Centres embedded within the NHS. There are currently 17 MND Care and Research Centres. At a recent meeting of the UK MND Care Centre workers and at the Association of British Neurologists MND Special Interest Group (SIG) an agreement recognised the need to develop an evidence based gastrostomy practice. The network of the MNDA MND Care and Research centres along with other MND clinics provides an excellent opportunity to

prospectively evaluate gastrostomy practice within the UK and develop evidence based guidelines for gastrostomy use in MND.

Rationale

The current clinical practice with regard to gastrostomy use in patients with MND has not been evaluated. There is little evidence on the optimal timing and method for gastrostomy insertion in patients with MND. PROGAS is a prospective nation-wide study in the UK that will provide an evidence base to inform dysphagia and nutritional management of patients with MND.

7 Research Plan and Methodology

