7.5 Study Outcomes

Primary:

- i) *Difference in the mortality rate in the first month following gastrostomy in PEG and PIG/RIG patients.*

Secondary:

- i) *Difference in the complication rate (classified in groups according to seriousness and time of occurrence) following gastrostomy in PEG and PIG/RIG patients.*
- ii) *Median survival time from (a) placement of feeding tube, (b) symptom onset, and (c) time of diagnosis of the disease in PEG and PIG/RIG patients.*
- iii) *Nutritional status changes (weight and BMI) following gastrostomy in PEG and PIG/RIG patients.*
- iv) *Self-perceived quality of life changes (measured by MQOL, gastrostomy questionnaire and qualitative interviews) following gastrostomy in PEG and PIG/RIG patients.*
- v) *Change in carer quality of life as measured by MCSI and qualitative interviews.*

Analysis will also include looking into how factors, such as (a) respiratory status, (b) site of symptoms onset, and (c) stage of disease, influence safety and survival following gastrostomy in PEG and PIG/RIG patients.

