7.7 Data Analysis

Quantitative data analysis

All quantitative data will be managed and analysed using SPSS for Windows version 14.0 (SPSS Inc., 1998). Exploratory data analysis will be initially carried out to establish the distribution of all continuous and categorical variables. Descriptive statistics (means, standard deviations, percentages) will be used to describe the characteristics of the participating centres, the participants and all the main variables of the study. Non-parametric tests (Spearman rank correlation tests and Mann Whitney U tests) will be performed for non-normally distributed continuous variables. Cronbach's alpha (α) coefficients will be determined for the measures that will be used in the study (i.e., MQOL, MCSI, gastrostomy questionnaire) in order to establish their internal consistency.

Continuity corrected Chi-square (χ^2) tests will be performed to determine the difference in the first-month mortality rate and the complication rate following gastrostomy in PEG and PIG/RIG patients. The same tests will be also performed to determine the self-perceived quality of life changes following gastrostomy in PEG and PIG/RIG patients as well as to determine the changes in carer quality of life. Kaplan-Meier survival curves will be used to determine the median survival time from placement of feeding tube, symptom onset and time of diagnosis of the disease in PEG and PIG/RIG patients. Independent samples t-tests will be used to determine the nutritional status changes following gastrostomy in PEG and PIG/RIG patients. Predictors of survival (e.g., respiratory status, site of symptom onset, stage of disease) following gastrostomy will be determined using logistic regression analysis and Cox proportional hazards regressions analysis.

Qualitative data analysis

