PIG is a hybrid technique in which the stomach is punctured under fluoroscopic guidance, following which the oesophagus is catheterised in a retrograde fashion using a guide wire. A gastrostomy tube is then passed over the guide wire at the mouth end, down the oesophagus and out through the abdominal wall. Conscious sedation is used, usually with a combination of midazolam with either pethidine or fentanyl.

Variation at your centre (please, use the space below)

.....

.....

.....

.....

.....

Please add any other comments that you may have with regard to this study in the space provided.

.....

.....

.....

.....

.....

.....

.....

Please return to:

[name], Academic Neurology Unit, University of Sheffield,
[name]

Pre Gastrostomy Patient Evaluation

Coded participant number: _____

Date of evaluation: _____

Date referred for gastrostomy: _____

Age: _____ **Gender:** (please tick) Female Male

Date of onset of MND symptoms (weakness): _____

Date of MND diagnosis: _____

Date of first contact by MND Centre: _____

MND site of onset: (please tick) Limb Bulbar

Weight (Kg) _____ **Height (m)** _____

Weight at diagnosis or earliest previous recorded weight since MND diagnosis:

Weight (Kg) _____ **Date** _____

Most recent respiratory assessment: (please, as complete as possible)

FVC % _____ **SNIP** _____

Most recent gases (arterial or transcutaneous): Date recorded _____

pO2 _____ **pCO2** _____ **O2 sats** _____

Indication for gastrostomy: (please, tick any that apply)

Marked weight loss

Unsafe swallow

Recurrent aspiration

Prolonged and difficult meals

Other _____

What do you think the benefits of gastrostomy will be for this patient? *(please, tick Yes or No for each of the options provided)*

	Yes	No
Prolong survival		
Stabilise nutrition and hydration		
Reduce risk of choking		
Reduce risk of chest infection		
Reduce risk/prevent aspiration		
Ease the difficulties of feeding (e.g. anxiety)		
Alternative route for medication		
Improve quality of life		

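### The only weight analysis named in 7.7 does not test hypothesis v, and its unadjusted PEG versus PIG/RIG contrast ignores weight trend before the tube

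*Protocol*

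**What the plan says.** Section 4 (v) of the Protocol states the aim as a directional hypothesis about gastrostomy as such: "We hypothesise that gastrostomy feeding is associated with an improvement in nutritional status". Section 7.5, secondary outcome iii, turns this into a comparison by method: "Nutritional status changes (weight and BMI) following gastrostomy in PEG and PIG/RIG patients". Section 7.7 gives the test: "Independent samples t-tests will be used to determine the nutritional status changes following gastrostomy in PEG and PIG/RIG patients". Section 7.7 also allows Mann-Whitney tests for skewed continuous variables. The only regression models it names, logistic and Cox, are for predictors of survival.

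The background (section 6) describes the course without adequate feeding: "Patients with severe dysphagia experience malnutrition and dehydration; continued weight loss". It describes tube feeding as "preventing malnutrition and dehydration as well as stabilising body weight". One of the expected benefits listed on the pre-gastrostomy evaluation form (Appendix 2) is "Stabilise nutrition and hydration". The same form asks for "Weight at diagnosis or earliest previous recorded weight since MND diagnosis", with its date, beside the current weight and the date of evaluation. Neither 7.5 nor 7.7 gives that earlier weight a role.

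**The concern.** There are two gaps.

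- **The hypothesis has no test.** It concerns what happens to nutrition after a gastrostomy, whereas the named analysis concerns whether one insertion method differs from another.
- **The method contrast is unadjusted.** Patients are not randomised, and section 7.6 says most centres use only one type of procedure. If centres refer at different points in the illness, the groups may have been losing weight at different rates before the tube, and a plain comparison of later change inherits that difference.

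A further point concerns interpretation. Where the realistic benefit is that a falling weight levels off, raw change from baseline has no means of showing it. The findings are meant to feed guidelines, so a nutritional result that is untested, or that reflects pre-tube differences, would matter to readers even though the outcome is secondary.

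**Working it through.** The plan states no figure for weight change, so there is nothing to reproduce. The check is a reading of the sections plus arithmetic on assumed rates.

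**Step 1. What the t-test tests.** Let c1 and c2 be the mean weight changes in PEG and PIG/RIG. The null is c1 = c2. If both groups gain the same amount, or both lose the same amount, the expected difference is c1 - c2 = 0 either way. The test therefore carries no information on whether nutrition improves overall. BMI adds little: Table 1 records height only before the gastrostomy, so BMI change is weight change divided by a fixed height squared.

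**Step 2. Raw change and change against prior trend.** Let r be the rate of loss before the tube (kg per month) and k the proportion by which the tube reduces it. Over 3 months:

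- raw change = -3 × r × (1 - k)
- change against prior trend = raw change - (-3 × r) = 3 × r × k

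The rates below are assumptions.

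| r (kg/month) | k | Raw change (kg) | Against prior trend (kg) |
|---|---|---|---|
| 0.5 | 1 (halted) | 0 | +1.5 |
| 1.0 | 1 | 0 | +3.0 |
| 1.5 | 1 | 0 | +4.5 |
| 0.5 | 0.5 (halved) | -0.75 | +0.75 |
| 1.0 | 0.5 | -1.5 | +1.5 |
| 1.5 | 0.5 | -2.25 | +2.25 |

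For a patient with r = 0 the two measures agree. The last column also assumes that the earlier loss would have continued in a straight line.

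**Step 3. The method contrast.** Suppose, as an illustration, that both methods slow the loss by the same 0.25 kg per month, but the groups were losing 0.5 and 1.0 kg per month beforehand. Raw 3-month changes are -3 × (0.5 - 0.25) = -0.75 kg and -3 × (1.0 - 0.25) = -2.25 kg. The t-test sees a difference of 1.5 kg, which equals 3 × (1.0 - 0.5) and comes wholly from the pre-tube difference.

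**Step 4. Whether the data allow better.** The forms give dated weights: the earlier one, the one at enrolment, and those at about 3 and 12 months, with a last recorded weight for patients who died. The date of the procedure is on the peri-procedure form. Table 1 has no weight at the procedure itself, and the enrolment weight is taken around referral.

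**Step 5. Why a simple difference of two slopes is not the answer.** With earlier weight E, baseline B, follow-up F and intervals T1 and T2, the difference is (F - B)/T2 - (B - E)/T1. An error e in B shifts it by -e × (1/T2 + 1/T1). A baseline that is low by chance therefore makes the tube look better, and patients referred because of weight loss are more likely to have one.

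**The case against.** A reader might infer that the plan treats zero change as failure and would therefore reach the wrong conclusion about the tube. The documents do not support that. No section sets a reference point or success rule for hypothesis v, and the null of the one named test is equality between methods.

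Nor do the documents say that all patients arrive losing weight. The statement in section 6 is about severe dysphagia. Section 7.4 admits patients whatever the indication, and hypothesis iii expects some to have the tube early. Marked weight loss is only one of several indications on the form. A hypothesis bolder than a background sentence is not in itself a contradiction. The kilogram figures above are assumptions.

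It can also be said that 7.6 promises to examine how recorded variables, nutritional status among them, affect the outcomes, and that the parameterisation of change can be left to an analysis plan. That is fair as far as it goes. But the general promise names neither the prior trend nor any adjusted model for weight, and it supplies no test of hypothesis v. What 7.7 does fix is a two-group test that answers another question.

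The limits of the prior trend also stand: it may span a long interval, and it shares the baseline weight with the post-tube trend.

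**Conclusion.** The point holds in a limited form. The nutritional analysis fixed in 7.7 does not address hypothesis v, and as an unadjusted comparison of non-randomised groups it can carry over differences in pre-tube weight trajectory. Raw change alone could miss a benefit in patients who were losing weight beforehand.

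The size cannot be stated from the Protocol. Under the assumed losses of 0.5 to 1.5 kg per month, raw 3-month change and change against prior trend differ by 3 × r, that is 1.5 to 4.5 kg, whatever the effect of the tube. This rests on linear continuation of the earlier loss, which a study without an untreated group cannot verify, and it does not apply to patients whose weight was steady. The matter concerns one secondary outcome and leaves one-month mortality and its power untouched. It is worth correcting because the correction is nearly free.

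**What to change.** Amend 7.7 as follows.

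- **Method contrast.** Replace the t-test with a regression of post-tube weight (or change) on method. Adjust for baseline weight, the pre-tube rate of change (dated earlier weight to baseline weight), and the actual intervals from the recorded dates.
- **Hypothesis v.** Report the within-patient change against zero. As a supporting analysis, report it against the pre-tube trend from a mixed model using all dated weights, with a change of slope at the procedure date, and not as a simple difference of two slopes.
- **Limits to state.** The earlier weight may be remote and understate recent loss. Baseline weight is taken at referral, not at the tube, and is shared by both slopes, so some regression to the mean will remain. Follow-up weights come mainly from survivors.

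Rewording hypothesis v to include stabilisation as well as improvement is optional.

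The cost is analysis wording and modest programming. No new form or visit is needed, although patients without a dated earlier weight will have no pre-tube rate, and their number should be reported.
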